#### **7.2.7. Data Analysis**

##### **7.2.7.1. Demographics**

To better understand the potential differences in results between the databases, the database-specific study populations will be described using frequency tables and proportions by age group, sex, calendar time. Attrition diagrams summarizing the deletion of records and reasons for deletion will be created.

---

### **7.2.7.2. Reporting delays**

Timeliness is essential for monitoring. Therefore, we will study delays in reporting by comparing event dates with the date the event is first used in the dashboard for monitoring. The analysis will be restricted to events for which it is known when they were first used (i.e. events that are present in the updated dashboard at time  $I$ , but were not in the previous update at time  $I-1$ ). The distribution of reporting delays will be obtained by event type or group of events (events recorded at hospital vs. primary care; exposure events, health outcome events) and will be summarized using measures of central tendency (average or median, whichever is most appropriate) and measures of spread (standard deviation or inter-percentile ranges, whichever is most appropriate).

As the total reporting delay is an accumulation of time lost due the processes at the level of the healthcare system (e.g. the time it takes for hospitals to report back to the GP - healthcare level) and processes at the level of the databases (database level) we will also look at the time between the most recent end of follow-up dates in the population CDM files and the use of this data in the dashboard. This will inform us regarding the amount of delays at the database level.

[figure not shown]
This way, we will obtain the total reporting delays as well as the delays at database level, allowing us to derive the delays at healthcare level.

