## **7. RESEARCH METHODS**

### **7.1. System testing: measures of success**

The following criteria will guide the measurement of the level of success of POC1.2:

- **1. Feasibility:** at least 3 databases (i.e. 50% of the pre-identified databases) can provide data on coverage, benefits and risks for near real-time monitoring (meeting criteria 2 and 3 below) to demonstrate the feasibility of vaccine benefit-risk monitoring in Europe.
- **2. Frequent refresh rates:** at least 3 databases can provide weekly (most successful), bi-weekly (highly successful) or monthly (successful) data on coverage, benefits and risks.
- **3. Timeliness:** at least 3 databases can provide data of 1 week (most successful), 2 weeks (highly successful), 1 month (moderately successful) or 2 months (minimally successful) old. The timeliness of the monitoring will be based on the distribution of the 'reporting delays': time between event date

---

and dashboard system date (i.e. date when new events that happen during the monitoring phase are displayed for the first time on the dashboard).

- 4. Acceptability of the approach by all ADVANCE stakeholders: the link to the monitoring dashboard will be shared with all ADVANCE stakeholders. A semi-structured survey and discussions will be organised to collect feedback. The ADVANCE consortium and the scientific advisory board (see section 7.2.10.2) will discuss and judge the successfulness of the POC1.2 study, discussing strengths, limitations and areas for further improvement.

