***Denmark: SSI/AUH\****

In Denmark national registry data are assembled and linked for specific studies according to the scientific question. Overall, the Danish Civil Registration System (CRS) database comprises individual level information on birth date, gender, vital status and sequential dates of migration of all residents in Denmark, i.e. approx. 5.6 mill. persons in a year, and an accumulated number of approx. 7.5 mill. persons over the period 1996-2014. Hence, using a unique personal identifier assigned to all Danish residents upon birth or immigration makes it possible to link the CRS with health care databases such as the Danish Vaccination Registry (DVR) and the Danish National Patient Registry (DNPR).

The national childhood vaccination database was established in 2000. This comprises information on all vaccinations administered to children below the age of 18 years, including vaccinations recommended by the Danish childhood vaccination programme, such as HPV, influenza etc. From November 2015, GPs and

---

others authorized to vaccinate have an obligation to record all vaccinations, and this information is now merged with data that were compiled before 2015 into the Danish Vaccination Registry.

The Danish National Patient Registry has recorded every inpatient hospitalization since 1977, and every outpatient and emergency room visit since 1995. For each admission, one primary and potentially several secondary diagnoses are registered, classified according to the *International Classification of Diseases, Eighth Revision* (ICD-8) until the end of 1993, and *Tenth Revision* (ICD-10) thereafter. In Advance this database is used to identify events.

While CRS and DVR are updated on a daily basis, DNPR have a delay of up to 3 months. The data are kept at the Research Services at the SSI from where access can be granted provided that the analysis has been reported and approved by the Danish Data Protection Agency. There is a long tradition of epidemiological studies in Denmark based on the health care databases that were proven valid for research.

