**Table S14.1: Patients.txt**

Name of the Variable	Description of the Variable	Format / Possible Values	Description of the Values
PatientID	Patient Identifier	any string maximum length: 32 characters	
Birthdate	Date of birth	YYYYMMDD.	
Gender	Gender	F M	Female Male
Startdate	Date from which the patient is eligible to be included in the study. This is typically the date the patient is entered into the registration system (date of registration with insurance/region, date GP started to collaborate). Run in periods should not be applied when defining StartDate	YYYYMMDD.	
Enddate	Date after which the patient is no longer eligible for inclusion in the study (e.g. end of registration with GP/database, insurance, moving out, death, last data draw down (whichever is earliest)).	YYYYMMDD.	

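### The healthcare-level reporting delay is obtained by a subtraction that leaves the wait for the next extract in it, on average half a refresh interval

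*Protocol*

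**What the plan says.** Protocol section 7.2.7.2 measures total reporting delay by "comparing event dates with the date the event is first used in the dashboard for monitoring". Only events whose first appearance can be dated are counted, in the protocol's words: "The analysis will be restricted to events for which it is known when they were first used". In practice these are events present in one update of the dashboard and absent from the update before it.

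The section names two contributors to that total. One is the healthcare system, with the example "the time it takes for hospitals to report back to the GP - healthcare level". The other is the database. The database contribution is measured as "the time between the most recent end of follow-up dates in the population CDM files and the use of this data in the dashboard". With the total and the database part in hand, the section concludes that the design works by "allowing us to derive the delays at healthcare level", that is, by difference.

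Two other places bear on this. Appendix 2, Table S14.1 defines the end date in the population file as the earliest of several dates, among them "moving out, death, last data draw down (whichever is earliest"; for a child still active this is the draw-down. Section 7.2.3, in the entry on Denmark, says of the linked registers: "While CRS and DVR are updated on a daily basis, DNPR have a delay of up to 3 months". It adds that the slower register, DNPR, is the one used to identify events.

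**The concern.** A delay from event to dashboard has at least three stages: the event gets recorded, the record waits for the next extract, and the extract is processed and displayed. The protocol measures the third stage directly and calls everything before it healthcare. The middle stage depends on how often the database is refreshed, which section 7.1 treats as a property of the database and grades under its second criterion.

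The anchor is also the population file alone. If the event source is less current than the population file, the difference in currency goes into the healthcare remainder too, wherever it arose.

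What is at stake is the diagnosis of delay. Section 5 lists, among the expected learnings, understanding why some databases cannot be used for monitoring. The split in section 7.2.7.2 is the quantitative tool the protocol offers for locating delay. As defined, it moves part of the database's own delay to the care setting, and moves more of it the less often a database refreshes.

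**Working it through.** The protocol gives no figure for the split, so there is none to reproduce. The check follows from its definitions.

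**Notation.** t is the event date. Load k is the load in which the event first appears. M_k is the latest end of follow-up in the population file of load k, which is the draw-down date (Table S14.1). D_k is the dashboard date of load k. R is the refresh interval.

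**Derivation from section 7.2.7.2.**
- Total delay = D_k − t
- Database part = D_k − M_k
- Healthcare part by difference = (D_k − t) − (D_k − M_k) = M_k − t

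The time from draw-down to dashboard cancels, so the result does not depend on it.

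**Refresh wait.** Section 7.1 accepts "weekly (most successful), bi-weekly (highly successful) or monthly (successful) data on coverage, benefits and risks", so R = 7, 14 or about 30 days. Assume event dates are spread evenly over the refresh cycle. An event recorded at once has t uniform between M_(k−1) and M_k, so M_k − t is uniform from 0 to R with mean R/2. With a true healthcare delay H, the mean becomes H + R/2. H is not given in the protocol; 0 and 10 days are assumed for illustration.

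| Refresh | R (days) | Derived mean, H = 0 | Maximum, H = 0 | Derived mean, H = 10 |
|---|---|---|---|---|
| Weekly | 7 | 3.5 | 7 | 13.5 |
| Bi-weekly | 14 | 7.0 | 14 | 17.0 |
| Monthly | 30 | 15.0 | 30 | 25.0 |

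A simulation of 400,000 events gave these same means with draw-down-to-dashboard times of 2 and of 5 days (both assumed). Limiting the window to about three months (12 weekly, 6 bi-weekly or 3 monthly loads), as section 7.2.5 does, left the H = 0 means unchanged. Two databases with identical care-setting reporting, one monthly and one weekly, would differ by 15.0 − 3.5 = 11.5 days in derived healthcare delay.

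**Source lag.** Let L be the lag of the event source behind the population source. If the population end date is not set back to match, the derived mean is H + L + R/2. With H = 0:
- L = 45 days (assumed midpoint): 48.5, 52.0 and 60.0 days for weekly, bi-weekly and monthly refresh
- L = 90 days (upper end of the SSI/AUH statement): 93.5, 97.0 and 105.0 days

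The amount misassigned through L is only the part of L that arises in the register rather than in hospital reporting. The protocol does not give that share, so the range is 0 to about 90 days.

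**Would setting the end date back help?** If a custodian sets the population end date to the completeness date of the event source, L moves into the database part. The remainder at H = 0 is still 3.5, 7.0 and 15.0 days. The refresh wait needs its own term.

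**The case against.** The strongest reply is that nothing graded depends on the split. Criterion 3 in section 7.1 uses the time from event date to dashboard date, and that total is the same however it is divided. No other success criterion uses the healthcare component, and section 7.2.7.3 rules out formal hypothesis testing. This stands. A reader might infer that the timeliness grades are biased by as much as the one-week top grade; the document does not support that. Nor is objective 1 in section 6 compromised: total delay and refresh rate answer it. The aim of understanding why databases fall short is in section 5.

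A reader might also infer that about 90 days of Danish database delay will be charged to healthcare. That is not established. Section 7.2.3 does not say whether the DNPR delay comes from late hospital submission, which would be healthcare delay in the protocol's own sense, or from register updating. Table S14.1 does not say which register sets the end date. The affected amount may be zero.

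Two mitigating points stand in part. Section 7.2.7.2 reports delays separately for hospital and primary-care events, and for exposures and outcomes, which would make a slow event source visible. Visibility does not assign the lag to a level, however. The refresh interval will also be known, so a reader could subtract R/2. That corrects a mean but not the medians and spreads the section also plans, and the section does not say it will be done.

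Finally, a figure in section 7.2.7.2 is missing from the available text and might draw a further component. The surrounding words describe only two.

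**Conclusion.** The point holds as a fault of attribution. The rule in section 7.2.7.2 yields M_k − t, which is not healthcare delay. It overstates healthcare delay by half a refresh interval on average: 3.5, 7 or about 15 days for weekly, bi-weekly or monthly refresh. Because the excess differs by schedule, the component cannot be compared across databases. This rests on two assumptions: event dates fall evenly over the refresh cycle, and the latest population end date is the draw-down, as Table S14.1 implies.

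The part concerning source lag is conditional. It applies where the event source is less current than the population file, for which SSI/AUH is the only documented case, and its size there lies between 0 and about 90 days.

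Total delay, the refresh criterion and the timeliness grades are untouched. The protocol itself fixes the derivation, so this is a stated rule to correct and not a detail left to the analysis plan. It should be corrected, but it does not threaten the study's main measures.

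**What to change.** Reword the second half of section 7.2.7.2. For each data stream, record the cut-off date M of every load, and split total delay into three parts that sum to it exactly. Here j is the first load whose cut-off is on or after the event date, and k is the load of first appearance:

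- extract to dashboard, database level: D_k − M_k
- refresh wait: M_j − t
- late arrival: M_k − M_j

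The sum is (D_k − M_k) + (M_j − t) + (M_k − M_j) = D_k − t.

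Late arrival takes only whole refresh intervals, so it should not be read event by event as the healthcare delay. With R = 30 and a true recording delay of 10 days, it reads 30 for one third of events and 0 for the rest. The mean, 30 × 1/3 = 10, is right, but the median is 0. For the distribution, treat the recording delay before extraction as interval-censored between max(0, M_(k−1) − t) and M_k − t. Do not report M_k − t as healthcare delay.

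Where the event source is less current than the population file, also record that source's own completeness date. Report the gap as a source lag whose origin the custodian states, assigned to neither level by default. Moving it wholesale to the database level would misplace any late hospital submission in the opposite direction. It is reported alongside the three parts, not added to them.

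The cost is one or two extra dates per load from each custodian, and a coarser estimate of healthcare delay, most noticeably with monthly refresh and the minimum of three loads.

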***United Kingdom RCGP\****

The RCGP's programme of influenza and respiratory disease surveillance has been supported by the Department of Health (DH) since 1967.

Between 1967 and 1993 the registered population within the RCGP RSC grew to 200,000 and it comprised 40 practices. By its 30th anniversary the population had risen to 570,000, with electronic links to general practices and laboratory data. The network exceeded 1million in 2015, and has now expanded to 237 general care practices and 2.4 million. From the start the network wanted clinicians to record a diagnosis in each consultation based on their clinical judgment; and only change that diagnosis if it adds to patient care. Diagnoses were originally recorded on paper written with "f", "n", or "o" written after- to designate first, new or an ongoing problem. This enabled incident and prevalent problems to be differentiated in routine data, vital for surveillance, but also for the Fourth National Morbidity Survey (MSGP4). High quality data recording was previously encouraged by visits to practices and quarterly feedback; now we apply principals of audit-based education to give practices personalized feedback on their data quality; we also provide use of on-line learning.

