**Italy: Pedianet\***

Pedianet ([www.pedianet.it](http://www.pedianet.it)) is a longitudinal observational DB that collects epidemiological clinical data for clinical research from family paediatricians involved in the Pedianet network in Italy. This system is based on the transmission of specific data from computerised clinical files, which the paediatricians in the network fill out during their daily professional activities. Informed consent is required from the parents. Such data is collected anonymously by a central server in Padua, where it is validated and elaborated.

Pedianet is an independent network. The coordination of the projects and data analysis is carried out by a scientific committee that include internationally renowned paediatricians, epidemiologists and researchers. Approximately 400 paediatricians throughout the country have taken part in Pedianet projects.

The paediatric population involves infants, toddlers, children and adolescents up to 14 years. The DB contains information on about 400 000 patients. This is the cumulative amount of patients who have ever been part of the dynamic cohort of patients who have been registered.

Pedianet includes primary care diagnoses, outpatient specialist diagnoses, hospital discharge diagnoses, prescribed drugs, vaccinations and laboratory test results.

In order to provide more comprehensive and validated data, linkage with external Regional databases, including hospitalizations, vaccinations and specialist visits/exams, is ongoing. PEDIANET is involved in several EU funded projects including TEDDY, GRIP, EU-ADR, EMIF and SOS. For the ADVANCE project, PEDIANET has linked the birth cohorts of 2006 and 2007 to the Regional Vaccination Register of Veneto on 9000 children. Linkage of subsequent birth cohorts is ongoing once consent is obtained from the subjects. Pedianet is listed in the ENCePP registry of datasources (<http://www.encepp.eu/encepp/viewResource.htm?id=20131>)

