### 13. APPENDIX 1: QUALITY ASSESSMENT

**Table: Assessment sheet for the quality /feasibility of the database to participate in the POC studies**

Quality of information				
META-DATA				
Category	Data	Measure(s)		Origin of information
Provenance of information	Sources for diagnoses (as codes or text) 
 
• primary care
 
• outpatient specialist
 
• hospital discharge
 
• emergency admission
 
• causes of death
 
	per type yes/no	Certain missingness?	Data provenance questionnaire to databases
	Vaccinations 
 
• routine childhood
 
• HPV
 
• travel
 
• influenza
 
• voluntary
 
 Drugs 
 
• prescribed/dispensed primary by GP
 
• prescribed/dispensed by specialist
 
• prescribed/dispensed during hospitalization
 
	per type yes/no	Certain missingness?	AIRR survey
	Diagnostic tests 
 
• primary care
 
• outpatient specialist
 
• during hospitalization
 
	yes/no	Certain missingness? Results?	AIRR survey
POPULATION				
Size	Number of lives (at any point in time) in population	N		Population fingerprint
	Number of subjects active at 1/1/2015	N		Population fingerprint
Dates	Missing Birthdate (no valid date entry (to be supplied by database owner))	N	Percentage on total number of lives	Attrition diagrams DBs
	Birth dates (day of birth independent of month)	Frequency of each day of the month of the DOB (1-31)	Percentage on total number of lives	Vaccine fingerprint (R)
Observation Time & lag time	Origin for the start of follow-up 
 
• birth (start of follow-up = birth)
 
• registration with database (start of follow-up > 1 month after date of birth)
 
	N	Percentage of total	Jerboa Event fingerprint
	Origin for the end of follow-up 
 
• death (end of follow-up = date of death in event file)
 
	N	Percentage of total	Jerboa Event fingerprint

	
 
exiting from database (end of follow-up < last data availability for practice)
 
	Median (5 th , 95 th percentile of lag time from date of delivery till last data)		

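### Where practices deliver data on different dates, the database-level delay in Section 7.2.7.2 is only a lower bound, and the healthcare-level delay derived from it is overstated by the same amount

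*Protocol*

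**What the plan says.** Section 7.2.7.2 of the protocol treats total reporting delay as the sum of a healthcare-level and a database-level part. Total delay is summarised by a measure of centre and a measure of spread. For the database-level part, the interval starts at "the most recent end of follow-up dates in the population CDM files" and ends when the data are used in the dashboard. Its purpose is stated as "This will inform us regarding the amount of delays at the database level", and the split is completed by difference, "allowing us to derive the delays at healthcare level".

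The end-of-follow-up date is defined in Appendix 2, Table S14.1. It is the earliest of several dates, and the list closes with "last data draw down (whichever is earliest". For a child still registered, it is therefore the last draw-down.

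Appendix 1 treats last data availability as a property of the practice when it classifies exits. In the same block it asks for the median with the 5th and 95th "percentile of lag time from date of delivery till last data".

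Section 7.2.3 describes three of the six databases as networks of practices. RCGP "has now expanded to 237 general care practices and 2.4 million" people. SIDIAP has 286 primary care practices. For PEDIANET, "Approximately 400 paediatricians throughout the country have taken part in Pedianet projects", which is not a count of those now active.

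**The concern.** Read naturally, the rule takes the latest end date in each population file. If practices deliver on different days, that date is set by whichever practice delivered last before the extract. Practices that are weeks behind have no influence on it.

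The subtraction makes this more than a question of presentation. Any database-level delay that the latest date misses is credited to the healthcare level. Slow delivery from practices to the database would then be reported as slow recording in the healthcare system. The first expected learning in Section 5 is to understand why some databases cannot be used for monitoring, and a wrong split points to the wrong cause. Section 7.2.7.2 asks for centre and spread of the total, but fixes neither for the component it subtracts.

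**Working it through.** The protocol gives no figure for database-level delay, so there is none to reproduce. The check asks how far the latest date can sit from the typical practice.

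**Inputs from the protocol.** n = 237 practices (RCGP), 286 (SIDIAP), about 400 (PEDIANET, ever taking part).

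**Assumed, because not stated.** The distribution of practice lags L (extract date minus the practice's last-data date), independent between practices; processing and transfer time P = 7 days from extract to dashboard.

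**Formulas.** Measured delay = min(L) + P. Typical delay = median(L) + P.
- Exponential lags with median m: mean = m / ln 2, and expected minimum = mean / n. For m = 28: 28 / 0.693 = 40.4, and 40.4 / 237 = 0.17 day.
- Uniform on 0 to 28 days: expected minimum = 28 / (n + 1) = 28 / 238 = 0.12 day.
- A 14-day floor plus an exponential with median 14: 14 + 20.2 / 237 = 14.1 days.
- Lognormal, median 28, log-SD 0.5: 7.0 days, by simulation with 4,000 replicates.
- Common draw-down 28 days old: 28 days.

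**Results for n = 237, P = 7 days**

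| Assumed lag pattern | Measured | Typical | Shortfall |
|---|---|---|---|
| Exponential, median 28 d | 7.2 | 35 | 27.8 |
| Uniform 0–28 d | 7.1 | 21 | 13.9 |
| Lognormal, median 28 d | 14.0 | 35 | 21.0 |
| 14-d floor + exponential, median 28 d overall | 21.1 | 35 | 13.9 |
| Common draw-down, 28 d | 35 | 35 | 0 |

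With 286 and 400 practices the minima, before P, are 0.14 and 0.10 day (exponential), 0.10 and 0.07 (uniform), 6.8 and 6.5 (lognormal), and 14.1 for both (floor). The number of practices matters little. The shape of the lag distribution near its lower end matters most.

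**Effect on the split.** Take the exponential case and assume a true mean healthcare delay of 7 days, with events spread over practices in equal proportion.
- True mean total = 7 + 40.4 + 7 = 54.4 days.
- True mean database-level delay = 40.4 + 7 = 47.4 days; measured = 7.2 days.
- Derived healthcare delay = 54.4 − 7.2 = 47.2 days, against a true 7.
- The overstatement, 47.2 − 7 = 40.2 days, equals the understatement, 47.4 − 7.2 = 40.2 days.

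With exponential lags of median 14 days (mean 20.2), the measured value is 7.1 against a true 27.2 days, and the derived healthcare delay is 27.1 against 7.

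**The case against.** A reader might infer that the measure is close to zero in every network whatever the typical practice does, and so cannot rank databases. The documents do not support that:
- The interval runs to dashboard use, so it includes the local programs and the transfer described in Section 7.2.9.
- Minima near zero arise only under lag distributions that let some practices be current at extraction. The lognormal and floor patterns above do not.
- No section says that practices deliver on different dates. SIDIAP is described as updated annually with central checks, which may amount to a common draw-down.
- ASLCR, ARS and SSI/AUH are linked or registry sources, so the mechanism concerns at most three of six databases.
- Success criterion 3 in Section 7.1 rests on the distribution of total delay from event to dashboard. New events from slow practices enter that distribution with their long delays.

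All of this stands and limits the point. Three further arguments carry less weight. First, the wording has plural dates and files, so one maximum per file is a reading rather than a certainty. But the plural fits several databases and loads, and if it is ambiguous it needs settling, since the readings can differ by weeks. Second, the analysis plan may choose the summary statistic, but the protocol itself fixes the starting date and the subtraction. Third, the Appendix 1 percentiles belong to the quality assessment and run to delivery, not to dashboard use. Their absence from Section 7.2.7.2 is therefore no contradiction; they only show that the practice-level date is a recognised quantity.

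One argument for the latest date is sound: exits and deaths do not disturb it, whereas a median of raw end dates would absorb every exit since 2014.

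**Conclusion.** The point holds in a limited form. Where practices deliver on different dates, the rule in Section 7.2.7.2 gives the freshest practice's lag plus processing time. That is a lower bound on typical database-level delay, and the derived healthcare-level delay is too high by the same amount. Under the assumed staggered patterns the shortfall against the median practice is about 14 to 28 days; under a common draw-down it is zero. The true size is unknown, because the documents state neither the spread of delivery dates nor the processing time. The harm is confined to the descriptive split between database and healthcare level. It does not reach total reporting delay or success criterion 3, and it does not show that the databases could not be compared on timeliness.

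**What to change.** In Section 7.2.7.2, have each custodian supply, at every data load, the last-data-availability date of each contributing practice, the date Appendix 1 already uses to classify exits. Report dashboard date minus that date per database as median with 5th and 95th percentiles. Use this distribution, not the most recent date alone, to split total delay. Give its mean as well, because means subtract exactly and medians in general do not.

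If a custodian cannot supply practice-level dates, keep the present figure but label it a minimum database-level delay, and label the derived healthcare-level delay a maximum.

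The cost is one small extra local aggregate table per load. The figures cannot simply be read from Patients.txt, which holds neither a practice identifier nor a reason for end of follow-up.
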